## 2. ABBREVIATIONS

ARDS	Acute Respiratory Distress Syndrome
BAL	Bronchoalveolar Lavage
CI	Confidence Interval
CRF	Case Report Form
eCRF	electronic Case Report Form
CT	Computed Tomography
EORTC	European Organization for Research and Treatment of Cancer
GM	Galactomannan
GCP	Good Clinical Practice
ICU	Intensive Care Unit
IPA	Invasive Pulmonary Aspergillosis
MSG	Mycoses Study Group
PCR	Polymerase Chain Reaction
SAPS3	Simplified Acute Physiology Score
SOFA	Sequential Organ Failure Assessment

### 3. PROTOCOL SUMMARY

- Title:** Prevalence of Influenza Related Invasive Aspergillosis; A Multicenter Prospective Observational Cohort Study
- Overview:** A multicenter prospective observational study conducted at 12 intensive care units in Sweden. All patients >18 years of age with a PCR-verified influenza A or B diagnosed up to 7 days before admission to the ICU or during ICU care, will be included in the study. A new clinical routine will be implemented: During the ICU stay screening with Beta-D-glucan and Galactomannan in blood/serum will be performed twice weekly and a respiratory sample will be retrieved for fungal culture and microscopy once weekly. All results from collected samples will be available to the patient responsible physicians. Clinical and microbiological data will be collected, and the diagnosis of invasive aspergillosis will be made using predefined diagnostic criteria.
- Objectives:**
1. To determine the prevalence of influenza-related invasive pulmonary aspergillosis in Swedish intensive care units
  2. To assess the clinical impact of and risk factors for influenzarelated invasive pulmonary aspergillosis
- Population:**  $\geq 18$  years of age. Confirmed influenza A or B diagnosed <7 days before admission to the ICU or during ICU stay. At least 50 patients will be enrolled in the study.
- Number of sites:** 12
- Study duration:** 1 year
- Enrolment:** Until the end of April 2020 if  $\geq 50$  patients have been enrolled. Enrolment will continue until  $\geq 50$  patients have been recruited.

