Effective treatment for Aspergillus is available and must be started promptly in cases of suspected IPA. If left untreated, IPA is associated with significant mortality.

The reports of influenza-related IPA have led the Netherland national guidelines to recommend that all influenza patients admitted to the ICU should undergo bronchoscopy with BAL sampling for Aspergillus diagnostics [9]. In Sweden, 300-400 influenza patients are annually admitted to intensive care units. Swedish data on the prevalence of aspergillosis are lacking, and there is a risk that IPA remains both an unknown and underdiagnosed complication of influenza infection in Swedish intensive care units.

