## **5.2 Scientific Rationale**

IPA is associated with significant mortality, and routine tests are often incapable of diagnosing the infection. The infection may, therefore, remain undetected without specific testing aimed to diagnose IPA. Reports of influenza-related IPA has emerged from several parts of the world. Still, the prevalence cannot be assumed to be equal in different settings as the transmission is dependent on exogenous exposure.

By accounts of the accumulated evidence, a new clinical routine will be introduced at study centers; Patients  $\geq 18$  years of age admitted to ICU with PCR-verified influenza A or B will be routinely tested to diagnose IPA early. The study will collect clinical and microbiological data of the patients subject to this new clinical routine. If the study provides evidence of IPA prevalence similar to the published reports, the clinical importance would be significant. New national guidelines regarding testing of influenza patients admitted to the ICU should be created with the potential to save both life and reduce suffering.

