## **7. STUDY DESIGN**

### **7.1 Study overview**

The study is a Swedish, nationwide, multicenter, prospective observational cohort study to determine the prevalence of IPA among patients admitted to the ICU with confirmed influenza infection.

A new clinical routine regarding IPA-testing will be implemented at the participating centers, similar to the current guidelines in the Netherlands. All samples will be retrieved and analyzed using local methods and logistics. All test results will be available to the patient responsible physician, who is free to act on them as deemed appropriate.

The study is non-interventional, no measurements or sampling will be made mandatory by the protocol and data collection at these pre-specified time-points will only take place if decided acceptable by the patient responsible physician. All aspergillus testing is part of the new clinical routine, and no additional sampling will be performed on accounts of the study.

All patients  $\geq 18$  years of age with confirmed influenza A or B diagnosed up to 7 days before ICU admission, or during ICU care, will be included in the study. Patient consent was waived in the ethics approval from *the Swedish Ethical Review Authority* (Dnr 201900557).

Recruitment is planned to begin in December 2019. Recruitment of patients is expected to stop in April 2020 if  $\geq 50$  patients have been recruited, or after that when 50 patients have been recruited.

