### **7.2 Study inclusion**

At least 50 patients will be enrolled in the study. The target sample size has been calculated using the expected prevalence of 15% IPA. The sample size is then sufficient to describe the prevalence with 10 % margin of error at the 95% confidence level. Approximately 100 influenza patients are admitted to ICUs of the participating centers every influenza season.

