**Radiological criteria:**

Any infiltrate on pulmonary imaging by portable chest x-ray or CT-scan of the lungs.

**Mycological criteria:** One of the following findings:

- Positive microscopy or culture of *Aspergillus* from BAL
- Galactomannan optical index on BAL >0,8
- Galactomannan optical index on serum  $\geq 0,5$

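### Probable IPA credits culture and microscopy only from BAL, but the routine as described asks for an unspecified respiratory sample, so the primary prevalence depends partly on discretionary BAL use

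*Combined protocol and SAP*

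**What the plan says.** - **Routine.** Section 3 (Overview) schedules Beta-D-glucan and galactomannan in blood or serum twice weekly, and adds that "a respiratory sample will be retrieved for fungal culture and microscopy once weekly". The type of respiratory sample is not given, and galactomannan on that sample is not mentioned.
- **Discretion.** Section 7.1 has sites use their own methods and logistics, makes no sampling mandatory, and leaves collection to the responsible physician.
- **Case definition.** Section 11.2 requires clinical, radiological and mycological criteria for probable IPA. The mycological routes are "Positive microscopy or culture of *Aspergillus* from BAL", a BAL galactomannan index above 0.8, or a serum galactomannan index of at least 0.5.
- **Stated resemblance.** Section 7.1 calls the routine "similar to the current guidelines in the Netherlands". Section 5.1 reports that guideline as saying that all influenza patients in the ICU "should undergo bronchoscopy with BAL sampling for Aspergillus diagnostics".
- **Use of the result.** Section 5.2 says: "If the study provides evidence of IPA prevalence similar to the published reports, the clinical importance would be significant". Section 5.1 cites reports of 19% (432 patients) and up to 23%.

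**The concern.** The tests in the described routine and the tests that can make a case do not line up. A site that sends a non-BAL lower-airway sample every week follows Section 3 in full, yet Aspergillus grown from that sample does not count under Section 11.2. Which patients can be classified through a respiratory sample then depends on who has BAL, and that is left to each site and physician.

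Two results are exposed. The first is the primary prevalence, which Section 5.2 sets beside published figures and links to possible national guidelines. The second is the risk-factor analysis in Sections 6.2 and 12. Cases missed for want of BAL fall into the comparison group, and if BAL is commoner in ventilated patients, invasive ventilation could appear as a risk factor through ascertainment alone.

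**Working it through.** **1. The plan's own figure.** Section 7.2 states "At least 50 patients will be enrolled in the study", that "The target sample size has been calculated using the expected prevalence of 15% IPA", and that this is "sufficient to describe the prevalence with 10 % margin of error at the 95% confidence level". The single-proportion formula gives n = 1.96² × 0.15 × 0.85 / 0.10² = 48.98, so 49. The stated 50 reproduces; at n = 50 the half-width is 1.96 × √(0.15 × 0.85 / 50) = 9.9 points. This calculation treats every patient as correctly classified.

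**2. Routine against case definition.**

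| Test named in Section 3 | Can it meet the mycological criterion in 11.2? |
|---|---|
| Serum Beta-D-glucan | No |
| Serum galactomannan | Yes, at an index of 0.5 or more |
| Culture or microscopy, respiratory sample | Only if the sample is BAL |
| BAL galactomannan (not named in Section 3) | Yes, above 0.8, if done |

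Without BAL, one route to probable IPA remains. Proven IPA (Section 11.1) is a separate route that needs a needle aspirate or biopsy.

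**3. What is recorded.** The ICU-discharge items in Section 9.1 include positive culture or microscopy without specimen type, and galactomannan in BAL or serum. No listed item records whether BAL was performed. Section 12 has no analysis by BAL status or qualifying route. As listed, the data items and analyses would not show how far BAL use drove the estimate.

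**4. Illustrative size.** Let P be true prevalence, f the share of patients with BAL, b the sensitivity of BAL testing and s that of serum galactomannan. With perfect specificity, independent tests and BAL use unrelated to IPA:

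observed = P × [s + (1 − s) × f × b]

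P = 0.19 comes from Section 5.1. The documents do not give b, s or f; I assume b = 0.9 and s = 0.30 to 0.65.

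| BAL share f | s = 0.30 | s = 0.65 |
|---|---|---|
| 30% | 0.19 × (0.30 + 0.70 × 0.27) = 9.3% | 0.19 × (0.65 + 0.35 × 0.27) = 14.1% |
| 50% | 0.19 × (0.30 + 0.70 × 0.45) = 11.7% | 0.19 × (0.65 + 0.35 × 0.45) = 15.3% |
| 90% | 0.19 × (0.30 + 0.70 × 0.81) = 16.5% | 0.19 × (0.65 + 0.35 × 0.81) = 17.7% |

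The whole swing from no BAL to BAL in every patient is P × b × (1 − s): 0.171 × 0.70 = 12.0 points at s = 0.30, and 0.171 × 0.35 = 6.0 points at s = 0.65. The planned margin is 10 points. Enrolling more patients does not reduce this shift.

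**5. Dependence on one assumption.** Strictly, f is the BAL share among true cases. If 30% of all patients but 70 to 90% of true cases had BAL (also an assumption), the observed figure would be 0.19 × (0.30 + 0.70 × 0.63) = 14.1% at the low end and 17.7% at the high end.

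**The case against.** Several points on the other side stand and limit the claim.

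- Serum galactomannan meets the mycological criterion alone and is scheduled twice weekly, so the prevalence does not rest on bronchoscopy alone.
- Physicians see all results and may act on them. A positive Beta-D-glucan or aspirate culture could prompt BAL, which would shrink the shortfall, as step 5 of the working shows.
- Limiting culture to BAL can be a deliberate choice for specificity. Section 5.1 says microbiological tests cannot separate colonisation from infection, and dyspnoea plus any infiltrate meets the other two criteria. A colonised patient with a positive BAL culture counts as a case, so the 11.2 figure can also err upward. A reader might infer that it is a strict lower bound; that does not follow.
- A reader might also conclude that the result cannot be compared with the 19% and 23% reports. The documents give neither BAL rates nor case definitions for them, so comparability is unverified, not excluded.
- Section 5.2 draws an inference only from a similar prevalence and states no rule for a lower one. Misreading a low estimate is a foreseeable risk, not a stated plan.
- The Section 8 workflow has no content in the text available for this review and may specify the sample. The statement that BAL galactomannan is not named applies to the description in Section 3.

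None of this removes the mismatch between Sections 3 and 11.2, or supplies the data needed to judge its effect.

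**Conclusion.** The concern holds in a limited form, as a cheap improvement. With the routine as Section 3 describes it and the criteria as Section 11.2 sets them, the primary prevalence depends partly on discretionary, site-specific BAL use and is likely to under-ascertain cases where BAL is not done. Comparability with the published reports is not established, and risk factors linked to BAL use, such as invasive ventilation, may be distorted in the same way.

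The size is unknown. The illustrated range, from about 9% to nearly 18% for the same true 19%, rests wholly on the assumed sensitivities and BAL shares, perfect specificity, independence of the tests and BAL use unrelated to IPA. The documents do not support the stronger conclusion that the estimate merely measures bronchoscopy practice, or that the study would declare IPA rarer in Sweden.

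**What to change.** 1. **Data and analysis.** Keep the 11.2 prevalence as primary. In Section 9.1, record the specimen type of each positive culture or microscopy, and for each patient whether BAL and BAL galactomannan were done. In Section 12, pre-specify prevalence by BAL status and by qualifying route. Add a secondary sensitivity prevalence that also accepts Aspergillus culture or microscopy from any lower-airway sample, other criteria unchanged. Present it as a broader, less specific figure and not as an upper bound, because it does not recover cases that only BAL galactomannan would detect.
2. **Wording.** Reconcile Sections 3, 5.1, 7.1 and 11.2 on sample type, since 7.1 likens the routine to a guideline that 5.1 describes as BAL for all. Which sampling applies is for the sponsor to state.
3. **Interpretation.** Say in Section 5.2 that a primary estimate below the published figures will be read in light of the BAL rate, and will not by itself be taken as a lower prevalence in Sweden.

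The cost is a small addition to the data form, a few extra estimates and some wording. Section 9.1 already plans a record review for microbiological findings, from which specimen type can be sought. No clinical rule changes. The downside is that the secondary figure may include colonisation, which is why it stays secondary.

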## 5. INTRODUCTION: BACKGROUND INFORMATION AND SCIENTIFIC RATIONALE

### 5.1 Background

Bacterial pneumonia is a well-known complication of influenza infection and contributes to both increased morbidity and mortality. A less known complication is a fungal infection with aspergillus species. Aspergillus is omnipresent and is commonly found in soil, dust, and food. We regularly inhale Aspergillus spores, but our immune system effectively takes care of the fungus, why disease does not occur [2]. Invasive pulmonary aspergillosis (IPA) has typically only been considered in immunosuppressed patients such as in haematological malignancies, hematopoietic stem cell transplantation, organ transplantation, or prolonged neutropenia [3]. Isolation of Aspergillus in respiratory samples from patients without these risk factors has been interpreted as colonization without any clinical relevance.

In recent years, several reports of influenza-related IPA in patients lacking classical risk factors have been published [4,5]. A possible explanation could be a viral injury to the respiratory epithelium as well as local and systemic lymphopenia [6]. The prevalence of IPA in influenza patients admitted to the ICU has been reported to be upwards of 23% [4]. In a large retrospective cohort study from the Netherlands and Belgium, published in The Lancet in October 2018, the prevalence of IPA was 19% among the 432 influenza patients admitted to the ICU [10]. The mortality was significantly higher among patients diagnosed with IPA. Most patients with influenza admitted to ICU lack classical risk factors for IPA and have, therefore, not been routinely investigated for IPA.

Aspergillus infections are challenging to diagnose and require specific culture media or the use of indirect diagnostic methods such as detection of Galactomannan in serum or BAL and detection of Beta-D-Glucan in serum. However, microbiological tests cannot distinguish between colonization and infection, which is why internationally recognized criteria that combine host factors, radiological signs, and microbiological findings have been published [7]. The infection is graded being confirmed, probable, or possible IPA. The criteria were originally developed for immunosuppressed patients, but modified criteria that are useful in the ICU has been published [8].

Effective treatment for Aspergillus is available and must be started promptly in cases of suspected IPA. If left untreated, IPA is associated with significant mortality.

The reports of influenza-related IPA have led the Netherland national guidelines to recommend that all influenza patients admitted to the ICU should undergo bronchoscopy with BAL sampling for Aspergillus diagnostics [9]. In Sweden, 300-400 influenza patients are annually admitted to intensive care units. Swedish data on the prevalence of aspergillosis are lacking, and there is a risk that IPA remains both an unknown and underdiagnosed complication of influenza infection in Swedish intensive care units.

## **5.2 Scientific Rationale**

IPA is associated with significant mortality, and routine tests are often incapable of diagnosing the infection. The infection may, therefore, remain undetected without specific testing aimed to diagnose IPA. Reports of influenza-related IPA has emerged from several parts of the world. Still, the prevalence cannot be assumed to be equal in different settings as the transmission is dependent on exogenous exposure.

By accounts of the accumulated evidence, a new clinical routine will be introduced at study centers; Patients  $\geq 18$  years of age admitted to ICU with PCR-verified influenza A or B will be routinely tested to diagnose IPA early. The study will collect clinical and microbiological data of the patients subject to this new clinical routine. If the study provides evidence of IPA prevalence similar to the published reports, the clinical importance would be significant. New national guidelines regarding testing of influenza patients admitted to the ICU should be created with the potential to save both life and reduce suffering.

## **5.3 Potential Risks and Benefits**

IPA testing is introduced as a clinical routine and is not part of the study. The study is a prospective observational cohort study where clinical and microbiological data of patients subjected to the new clinical routine will be collected and assessed. Study participants admitted to any of study centers will receive the benefit of routine IPA testing and the possibility of early intervention if IPA is diagnosed.

## **6. STUDY OBJECTIVES**

### **6.1 Primary objective**

To determine the prevalence of influenza-related invasive pulmonary aspergillosis in Swedish intensive care units.

### **6.2 Secondary objective**

To assess the clinical impact and risk factors related to influenza-related invasive pulmonary aspergillosis. Patients with proven or probable IPA will be compared to patients that do not meet the criteria for proven and probable IPA. Baseline characteristics and clinical data such as SAPS3, SOFA score, need for invasive ventilation and need for continuous renal replacement therapy, will be assessed to find risk factors for IPA.

## **7. STUDY DESIGN**

### **7.1 Study overview**

The study is a Swedish, nationwide, multicenter, prospective observational cohort study to determine the prevalence of IPA among patients admitted to the ICU with confirmed influenza infection.

A new clinical routine regarding IPA-testing will be implemented at the participating centers, similar to the current guidelines in the Netherlands. All samples will be retrieved and analyzed using local methods and logistics. All test results will be available to the patient responsible physician, who is free to act on them as deemed appropriate.

The study is non-interventional, no measurements or sampling will be made mandatory by the protocol and data collection at these pre-specified time-points will only take place if decided acceptable by the patient responsible physician. All aspergillus testing is part of the new clinical routine, and no additional sampling will be performed on accounts of the study.

All patients  $\geq 18$  years of age with confirmed influenza A or B diagnosed up to 7 days before ICU admission, or during ICU care, will be included in the study. Patient consent was waived in the ethics approval from *the Swedish Ethical Review Authority* (Dnr 201900557).

Recruitment is planned to begin in December 2019. Recruitment of patients is expected to stop in April 2020 if  $\geq 50$  patients have been recruited, or after that when 50 patients have been recruited.

### **7.2 Study inclusion**

At least 50 patients will be enrolled in the study. The target sample size has been calculated using the expected prevalence of 15% IPA. The sample size is then sufficient to describe the prevalence with 10 % margin of error at the 95% confidence level. Approximately 100 influenza patients are admitted to ICUs of the participating centers every influenza season.

### **7.3 Inclusion criteria**

Patients must meet all the inclusion criteria to be eligible for the study:  $\geq 18$  years of age, PCR-verified influenza A or B diagnosed within 7 days of ICU admission, or during ICU stay.

#### **7.4 Exclusion Criteria**

Patients  $\leq 18$  years of age cannot be enrolled in the study as the evidence motivating the implemented routine IPA testing does not contain patients under 18 years of age.

#### **7.6 Screening**

Influenza testing will be performed on the basis of clinical suspicion, and part of routine care.

#### **7.7 Informed consent**

This is a non-interventional study and the need for informed consent was waived in the approval from the Swedish Ethical Review Authority (DNR (Dnr 201900557))

## 8. WORKFLOW: OVERVIEW

## 9. DATA COLLECTION

All patient responsible physicians in the participating ICUs will be eligible to enrol patients in the study. All participating ICUs will receive both written and oral instructions about the study from the study site investigator. Data will be obtained from the participant's medical records and initially entered on a paper CRF. The empty CRF will be made available by sending prepared folders to the study sites. Additional CRFs will be made available for print from study website ([piraiastudy.se](http://piraiastudy.se)). Study site investigators will then enter the collected data into a web-based eCRF. The procedure will ensure continuous monitoring of the collected data.

### 9.1 Data to be collected Baseline

#### characteristics

Date of ICU admission

Age

Sex

SAPS3-score on arrival to the ICU SOFA-

score on arrival to the ICU Presence of:

Liver cirrhosis (defined as Child-Pugh-score  $\geq$ A)

Heart failure (defined as ejection fraction  $<$ 40%)

Diabetes mellitus (not diet treated)

Renal failure (defined as creatinine clearance  $<$ 30 mL/min/1.73m^2)

Body Mass Index  $>$ 30 kg/m^2

Haematological malignancy

Hematopoietic stem cell transplantation

Organ transplantation

Daily smoking in the last year

Solid tumour

Neutropenia (defined as  $<$ 0,5 x10^9 neutrophils)

Chronic obstructive pulmonary disease

New lung infiltrate

Treatment with corticosteroids in the last 28 days

Treatment with corticosteroids in a dose equal to or above 15 mg/day prednisone

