## **12 STATISTICAL ANALYSIS**

Prevalence of Proven/Probable IPA will be calculated at the 95% confidence level. Patients meeting the criteria for proven/probable IPA will be compared to the influenza positive patients who do not meet the criteria, in terms of underlying risk factors and outcome measures. Categorical variables will be assessed by Fischer exact test and  $X^2$  test, and continuous variables with t-test or Mann Whitney U test where appropriate. We will also perform multivariable analysis by binary logistic regression to detect independent risk factors for IPA. All analyses will be conducted using a threshold of 95% confidence level (P-value 0.05). ICU mortality and 90 days after admission to the ICU mortality will be compared using survival analysis.

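### BMI and renal function are listed only as above or below a cut-off; recording the values would keep more power for these two factors if IPA risk changes smoothly with them

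*Combined protocol and SAP*

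**What the plan says.** The baseline list in section 9.1 places two quantities that are numerical by nature among items to be marked as present: "Body Mass Index" above 30 kg/m2, and "Renal failure (defined as creatinine clearance" below 30 mL/min/1.73m2. No section collects BMI, height, weight, creatinine or clearance as a number. Age, SAPS3 and SOFA in the same list carry no cut-off.

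Section 9 gives the source: "Data will be obtained from the participant's medical records", first on a paper form and then in the eCRF. Section 12 assigns Fisher's exact and chi-square tests to categorical variables and "continuous variables with t-test or Mann Whitney U test where appropriate". It adds a binary logistic regression for independent risk factors. Finding risk factors is the secondary objective (section 6.2), and section 11 compares every recorded baseline characteristic by IPA status.

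The sample size in section 7.2 rests only on the precision of the prevalence: "At least 50 patients will be enrolled in the study", with an "expected prevalence of 15% IPA" and a "10 % margin of error at the 95% confidence level". No power is stated for the risk-factor comparisons.

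**The concern.** A variable cut in two keeps only the side of the line on which each patient falls. If the risk of IPA rises or falls gradually with body mass or renal function, patients far from the cut-off carry information that the split throws away. The tests for continuous variables in section 12 cannot then be used for these two factors.

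The plan expects few IPA cases, so each comparison has little power to begin with. At stake is the chance of detecting a real association with either factor, under a stated secondary objective. BMI has to be known or calculated before the item can be answered, so the number is normally at hand when the form is completed.

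**Working it through.** **The plan's own figure.** Precision formula for a proportion: n = z² p(1−p)/d² = 1.96² × 0.15 × 0.85 / 0.10² = 48.98, so 49. The stated minimum of 50 is reproduced. At n = 50 the half-width is 1.96 × √(0.15 × 0.85/50) = 0.099.

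**Expected cases.** At the minimum, 0.15 × 50 = 7.5, taken as 8 against 42 (95% binomial range 3 to 13 cases). Section 7.2 adds: "Approximately 100 influenza patients are admitted to ICUs of the participating centers every influenza season". If all were enrolled, 0.15 × 100 = 15 against 85.

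**Assumptions not in the documents.** The factor is normally distributed. IPA patients are shifted by d standard deviations. A share q of non-IPA patients (10% to 40%) lies beyond the cut-off. The test is two-sided at 0.05; section 12 gives 0.05 but not the sidedness.

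**Information kept by a cut-off.** For a small shift the efficiency is φ(c)²/[q(1−q)], where c is the normal quantile at 1−q. At q = 20%, c = 0.842 and φ(c) = 0.280, so 0.0784/0.16 = 49%. The other values are 62% at q = 40%, 58% at 30% and 34% at 10%.

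**Power with the value kept.** Two-sample t-test, noncentrality d/√(1/n₁ + 1/n₂). For d = 0.8:
- 8 against 42: 0.8/0.386 = 2.07 on 48 degrees of freedom, power 53%.
- 15 against 85: 0.8/0.280 = 2.86 on 98 degrees of freedom, power 81%.

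**Power with the cut-off.** The share of IPA patients beyond the cut-off is Φ(d − c). For d = 0.8 and q = 20% this is Φ(−0.04) = 48%. Power comes from exact enumeration of all possible tables. Ranges are over q = 10% to 40%.

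| IPA / non-IPA | Shift | Value, t-test | Cut-off, Fisher | Cut-off, chi-square |
|---|---|---|---|---|
| 8 / 42 | 0.5 SD | 25% | 13-16% | 18-21% |
| 8 / 42 | 0.8 SD | 53% | 29-35% | 36-42% |
| 8 / 42 | 1.0 SD | 72% | 41-52% | 50-58% |
| 15 / 85 | 0.8 SD | 81% | 54-59% | 59-65% |

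The shift detectable with 80% power at 8 against 42 is 1.10 SD with the value and about 1.40-1.46 SD with the cut-off (Fisher, q = 10-30%).

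**Counter-case: risk steps at the cut-off.** Suppose 20% of non-IPA and 60% of IPA patients lie beyond it, with no gradient on either side. With 8 against 42, power is 59% (Fisher) or 66% (chi-square) for the split, and 44% for the t-test on the value. The ordering reverses.

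**The case against.** - **Scope.** A reader might infer that the risk-factor analysis as a whole loses much of its power. The documents do not support that. Most baseline items are naturally yes/no, and age, SAPS3 and SOFA are not cut. The figures above concern BMI and renal function. A few other items, such as neutropenia, are also set against a threshold, but nothing was computed for them.
- **Permanence.** It is tempting to say that the values are lost for good. Data come from medical records (section 9), records are reviewed for findings up to 90 days (section 9.1), and each site keeps a list linking study number to personal number (section 9.2). The values could probably be retrieved with a second pass through the records. The loss is one of effort and perhaps of permission.
- **Renal failure as a diagnosis.** The point that the value must already be known is firm only for BMI. Renal failure sits among comorbidities and might be marked from a charted diagnosis. A bare clearance figure could also mix pre-illness and ICU-admission function. This stands, so the item should be kept and a dated value added.
- **The size is assumed.** Normality, a smooth effect and the share beyond the cut-off are not in the documents. A 1 SD shift is very large: with 30% of non-IPA patients beyond the cut-off it implies 68% of IPA patients, an odds ratio of (0.68/0.32)/(0.30/0.70), about 5. At 0.5 SD the factor would probably be missed either way. With 8 against 42, Fisher's actual error rate is about 2-3% and that of chi-square 4-5%, so part of the Fisher gap is conservatism of the test. Chi-square still shows a loss.
- **A threshold effect favours the split.** True, but it is no reason to omit the number, because the category can be derived from it.
- **The form itself is not among the documents.** Section 9.1 is a list of data items. It indicates yes/no fields without showing them.

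**Conclusion.** The point holds for BMI and renal function, as a minor improvement. As listed, both can be analysed only as yes/no. If the relation with IPA is smooth, a 0.8 SD shift is detected with 53% power using the value, against 29-35% or 36-42% using the cut-off, at the minimum sample. A full season narrows the gap little: 81% against 54-59% or 59-65%. Eight cases is the expected number at the minimum enrolment, so a larger sample is possible.

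These sizes depend on the assumed distribution, share beyond the cut-off and shape of effect, and they reverse if risk truly steps at the threshold. What does not depend on them is that a recorded value allows both analyses and a yes/no item allows one. The small number of cases remains the main limit on the secondary objective. The primary prevalence estimate does not use these items.

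**What to change.** In section 9.1, and in the paper form and eCRF:
- Record BMI as a number, or height and weight.
- Keep the renal-failure item as it is, and add a creatinine or clearance value with its date.

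In section 12, state that both are analysed as continuous variables, in the group comparison and, if chosen as covariates, in the logistic model. The existing categories are then derived from the values for description.

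The cost is a few numeric fields, slightly more data entry and some missing values. No sampling is added, so the observational design is unchanged. The query process in section 10 already covers missing and out-of-range entries.
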